 - 3.3.3 To determine if hormone and growth factors [i.e., glucocorticoids (e.g., cortisol), gonadal steroids (e.g., estradiol, testosterone, progesterone),

growth hormone, human chorionic gonadotropin (hCG), insulin-like growth factor-1 (IGF-1), and neuronal growth factor (NGF)] may prove to be a predictor of radiation induced neurocognitive decline.

3.3.4 To validate the prognostic significance of a combined multi-molecular marker survival classifier called the Molecular Clinical Prognosticator (MCP).

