12.0 Statistical Considerations

- 12.1 Randomization procedure: A stratified block randomization procedure will be used. Randomization will be performed using CORe. The randomization strata are as defined above in section 7.0, and the block size will be 6. Patients who withdraw from the study after randomization, but prior to receiving treatment will be considered a cancel and replaced.
- 12.2 Sample size: With IMRT the cognitive function failure rate at 4 months is 45%, based off of comparative analyses of the cognitive failure rate of RTOG 0614 and compared to the cognitive impairment seen on RTOG 0525; we hope to demonstrate that IMPT can achieve a cognitive function failure rate at 4 months of only 30%. We assume the time to cognitive failure in each treatment arm follows an exponential distribution. A cognitive failure rate of 45% at 4 months then implies a median time to cognitive failure of 4.6 months, while a cognitive failure rate of 30% at 4 months implies a median time to cognitive failure to cognitive failure of 7.8 months.

We will use a 1-sided significance level of 0.20 as suggested by Rubinstein et al. [51]for phase II screening trials. We expect to enroll 2 patients per month, and we will randomize 60 evaluable patients (30 to each treatment arm). We will have 80% power to detect an improvement in cognitive failure at 4 months from 45% in the IMRT arm to 30% in the IMPT arm. We expect to observe 43 events, and the analysis will be performed once we have observed these events. We define evaluable patients as those who have received the assigned treatment *and* completed baseline and at least one follow-up neurocognitive testing. We expect we will need an over accrual of 33% to account for those patients not evaluable. Therefore the target total enrollment sample size is 90 patients to accrue a total of 60 evaluable patients. We expect to observe 43 events, and we expect the trial to take 41 months to observe these events.

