We will use descriptive statistics to summarize by treatment arm the quality of life data at each assessment time. We will also use boxplots to summarize the quality of life data by treatment arm at each assessment time. We will model the quality of life data using mixed effects regression methods with repeated measures. The model will include treatment arm, selected dosimetric parameters, baseline cognitive function, location of the primary tumor (left vs. right hemisphere, if bilateral disease is present, location will be determined by the hemisphere with highest burden of disease), and the stratification factors used at randomization as fixed effects and patient as a random effect. We will similarly analyze the cognitive tests. For nearly all the prior mentioned analyses we will also plan to conduct an as-treated analysis.

We will tabulate by treatment arm the adverse events by grade and relationship to treatment.

We will use logistic regression methods to model the logit of the probability of neurocognitive decline as function of ApoE (i.e., Apo E2, Apo E3, Apo E4) genotyping, inflammatory markers (i.e., IL-1, IL-6, TNF- α), and hormone growth factors (i.e., glucocorticoids, gonadal steroids, growth hormone, human chorionic gonadotrpin, insulin-like growth factor-1, neuronal growth factor).

Determination of MCP class will be determined by RPA analysis using results of MGMT, *IDH1*, G-CIMP, and mRNA assays as well as RTOG RPA class. We will use descriptive statistics to report class distributions overall and by treatment arm. Survival by classes will be visualized on Kaplan/Meier plots, compared by the logrank test. The Cox proportional hazards regression will be used to model MCP classification, adjusting for treatment arm and stratification factors.

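### The biomarker model in section 12.4 has about 11 to 16 coefficients, at most about 3 patients per coefficient, an undefined outcome, and no protection against overfitting or multiplicity

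*Combined protocol and SAP*

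**What the plan says.** Objectives 3.3.1 to 3.3.3 ask whether ApoE genotype, inflammatory markers, and hormones and growth factors predict radiation-induced decline. The analysis is one sentence in section 12.4: "We will use logistic regression methods to model the logit of the probability of neurocognitive decline as function of ApoE" genotype, followed in the same list by IL-1, IL-6 and TNF-alpha and by six hormone or growth-factor headings. Section 3.3.3 fills in those headings. It gives cortisol as an example of a glucocorticoid, names estradiol, testosterone and progesterone as examples of gonadal steroids, and continues with "growth hormone, human chorionic gonadotropin (hCG), insulin-like growth factor-1 (IGF-1), and neuronal growth factor (NGF".

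Section 12.4 does not say what counts as decline or by when, how ApoE is coded, whether markers enter together or singly, or which blood draw supplies the value. Sections 9.6, 10.3.2 and 10.3.3 have serum taken within the first five fractions and at every follow-up visit. No penalty, selection rule, internal validation or multiplicity rule is given. Section 12.4 also has secondary analyses run once on all patients and once on evaluable patients only. Section 12.2 plans 60 evaluable patients out of 90 enrolled and says: "We expect to observe 43 events, and the analysis will be performed once we have observed these events".

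**The concern.** In a logistic model the information is limited by the smaller outcome group, not by the total number of patients. Here that group is hardly larger than the number of coefficients. A maximum-likelihood fit then adapts to noise: coefficients come out too large and apparent discrimination is too good. Separately, about a dozen markers tested at 0.05 without adjustment will often produce a nominal finding by chance. Objectives 3.3.1 to 3.3.3 ask which markers predict decline, and blood is drawn at every evaluation to answer that. As planned, a reader could not tell a real predictor from a chance one.

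**Working it through.** **1. The plan's event count reproduces.** Section 12.2 says "With IMRT the cognitive function failure rate at 4 months is 45" per cent and hopes that "IMPT can achieve a cognitive function failure rate at 4 months of only 30" per cent. It adds: "We assume the time to cognitive failure in each treatment arm follows an exponential distribution". So HR = ln(0.70)/ln(0.55) = 0.597. With "We will use a 1-sided significance level of 0.20" and 80% power, Schoenfeld's formula gives 4(0.842 + 0.842)²/(ln 0.597)² = 42.5, rounded up to 43. This matches the plan.

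**2. Smaller outcome group (derived, not printed).** If decline is the primary-endpoint event at that cut, 60 − 43 = 17. These 17 would include patients who progressed or died first and patients still in follow-up, so not all are true non-decliners.

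**3. Coefficients (derived, not printed).** ApoE as three groups 2, inflammatory markers 3, hormones and growth factors 8 (cortisol 1, gonadal steroids 3, the other four 1 each): 2 + 3 + 8 = 13. With gonadal steroids as one term it is 11. With six ApoE genotypes (5 terms) it is 16.

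**4. Ratio.** 17/13 = 1.3.

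**5. Behaviour when no marker predicts.** Independent standard-normal markers were fitted jointly by maximum likelihood, 2,000 runs per setting (1,000 for the setting with 5 in the smaller group). For 17 versus 43 and 13 terms:
- Mean apparent AUC was 0.79 (5th to 95th percentile 0.71 to 0.88), when the truth is 0.50.
- The overall likelihood-ratio test at 5% rejected in 13% of runs; repeat simulations gave about 14%.
- At least one Wald p<0.05 occurred in 54%; repeat simulations gave 53%.
- Complete separation occurred in no run.

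A single noise predictor on the same split gave AUC 0.57 and 5% rejection. Eleven terms gave AUC 0.77 and 48% with some p<0.05; sixteen gave 0.83 and 64%. Two ApoE indicators with assumed group shares of 10/62/28% changed little.

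**6. How much of the 53% is sparsity?** For 13 independent tests at any sample size, 1 − 0.95^13 = 0.49. Simulating 600 patients with 430 failures (170/13 = 13 per coefficient) gave 48.5%. So most of it is multiplicity. Fitting the markers singly leaves 1 − 0.95^11 = 0.43 to 0.49.

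**7. Other definitions of the outcome, 13 terms.**

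| Definition | n | Smaller group | Per coefficient | Noise AUC | LR test rejects | Any p<0.05 |
|---|---|---|---|---|---|---|
| Evaluable, by 4 months: 30×0.45 + 30×0.30 = 22.5 | 60 | 22 | 1.7 | 0.78 | 12% | 58% |
| Evaluable entered by month 41: 41×2×60/90 = 54.7, less 43 | 55 | 12 | 0.9 | 0.84 | 18% | 53% |
| Evaluable, any time in 24 months: 30×0.55^6 + 30×0.70^6 = 4.4 non-decliners | 60 | 5 (simulated) | 0.4 | 0.94 | 48% | 1% |
| All, non-evaluable as failures, at 43 events | 90 | 17 | 1.3 | 0.77 | 11% | 53% |
| All, by 4 months: 90×0.375 = 33.75 | 90 | 34 | 2.6 | 0.72 | 9% | 55% |
| All, by 4 months, non-evaluable as failures: 90 − 22.5 − 30 = 37.5 | 90 | 38 | 2.9 | 0.72 | 9% | 55% |

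In the 24-month row, 47% of runs separated completely, so its Wald p-values mean little. Counting all 30 non-evaluable patients as non-failures gives 43/13 = 3.3 and AUC 0.72, but section 12.3 counts them as failures in the primary analysis.

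**The case against.** The strongest reply is that section 12.4 says neither that the fit is unpenalised nor that all markers share one model. The objectives are framed by marker family, so separate models are a fair reading, and the split of gonadal steroids into three comes from a list of examples. The 43-event trigger times the primary analysis and need not time this one. Apparent AUC is not a planned output. The objectives are correlative and worded as possibilities, and hypothesis-generating screens often go without multiplicity control.

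Much of this stands. Joint maximum-likelihood fitting is the natural reading of one function listing every marker, but it is a reading, and so are the 13 and the 17. It does not clear the plan. Separate fits remove the overfitting but leave a 43% to 49% chance of a false lead with independent markers. No definition of the outcome examined gives more than about 3 patients per coefficient with 13 terms. The missing definition is itself a gap.

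Three stronger readings are tempting and not supported:
- A reader might put the whole 53% down to too few patients per coefficient; step 6 shows otherwise.
- A reader might expect noise to pass the overall test as a rule; at 17 versus 43 it fails to reject in about 86% of runs.
- A reader might expect the fits to break down; at 17 versus 43 none separated, and separation becomes common only if decline means any failure within 24 months.

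**Conclusion.** The concern holds for the correlative marker analysis and should be corrected there. On the central reading (17 versus 43, 13 terms, joint maximum likelihood), sparsity lifts apparent AUC under the null to about 0.79 and the size of the overall test to about 14%. Unadjusted testing of many markers makes at least one false lead about as likely as not.

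This assumes normal, independent markers. For jointly normal markers, correlation would not change the AUC or likelihood-ratio results, because the fit is unaffected by linear recombination of the predictors. It would change the chance of at least one small p-value. The primary endpoint, its test and the sample size do not depend on this model, and nothing here casts doubt on them.

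**What to change.** Rewrite the biomarker paragraph of section 12.4 to:
- Define the binary outcome, its time point, and how progression, death and incomplete follow-up are handled.
- Fit the joint model by ridge-penalised logistic regression and report discrimination corrected for optimism by bootstrap, repeating the choice of penalty in each resample. Firth's penalty alone is not enough: in null runs at n = 60 its apparent AUC was 0.794, the same as maximum likelihood.
- Test single markers with false-discovery-rate control across all markers, at a stated level.
- Keep the E2/E3/E4 coding and state how mixed genotypes are grouped. An E4-carrier variable alone would lose the neuroprotection question in sections 3.3.1 and 5.2.1.
- Use only the first sample, within the first five fractions, as the predictor of later decline, because later draws can follow the decline they are meant to predict. Sections 5.2.2 and 5.2.3 place this sample before treatment, so the timing needs reconciling with section 9.6.
- Report serial marker values separately, as descriptive associations.

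The cost is a paragraph of SAP text, routine software and a little more analysis work. No visit, assay or sample size changes. The downside is fewer single-marker claims.

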3.0 Objectives

3.1 Primary Objectives

- 3.1.1 To assess whether treatment with IMPT results in longer time to cognitive failure compared with IMRT. Cognitive failure is defined as the first cognitive failure on any of the following six cognitive outcome variables: Hopkins Verbal Learning Test Revised (HVLT-R) Total Recall, HVLT-R Delayed Recall, HVLT-R Delayed Recognition, Controlled Oral Word Association (COWA), Trail Making Test (TMT) Part A or Part B.
- 3.2 Secondary Objectives
 - 3.2.1 To determine local control in the brain post radiation treatment.
 - 3.2.2 To determine overall survival in each treatment arm.
 - 3.2.3 To assess quality of life measured at two month intervals for a total of two years post-radiotherapy for both treatment arms.
 - 3.2.4 To assess the pattern of cognitive change in memory at two month intervals for two years post-treatment as well as executive function and processing speed.
 - 3.2.5 MRI diffusion weighted images (DWI) and reconstructed apparent diffusion coefficient (ADC) maps will be analyzed to see if there is a difference between pre- and post-treatment scans. These will also be analyzed for differences between the two treatment modalities.
 - 3.2.6 To evaluate if diffusion tensor imaging (DTI) correlates to the cognitive changes and if there are differences between the two treatment modalities.
 - 3.2.7 To assess the pre-treatment factors of recursive partitioning analysis (RPA) class and mini mental status examination (MMSE) in the predictive determination of local and distant control and cognitive outcome in each treatment arm.
 - 3.2.8 To assess the correlation between location of primary lesion, total volume of intracranial disease, and cognitive outcome in each treatment arm.
 - 3.2.9 To determine the relationship between MGMT promoter methylation status and cognitive and local control outcomes.
 - 3.2.10 To document and descriptively compare post-treatment adverse side effects between the two treatment arms.
 - 3.2.11 To determine the relation between dosimetric parameters and cognitive and local control outcomes.
- 3.3 Correlative objectives
 - 3.3.1 To determine if Apo E (i.e., Apo E2, Apo E3, and Apo E4) genotyping may prove to be a predictor of radiation induced neurocognitive decline (or neuro-protection).
 - 3.3.2 To determine if inflammatory markers (i.e., IL-1, IL-6, and TNF- α) may prove to be predictors of radiation induced neurocognitive decline.

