10.0 Criteria for Response and Toxicity

10.1 Definition of primary endpoint:

- 10.1.1 Time to cognitive failure on any of the 6 primary variables from the pre-specified cognitive tests (HVLT-R total recall, HVLT-R delayed recall, HVLT-R delayed recognition, TMT Part A or Part B, COWA) with failure defined as a decline that meets or exceeds the reliable change index (RCI) for each cognitive test variable. A cumulative incidence approach will be used to estimate median time to cognitive failure in order to account for the competing risks of disease progression and death. Patients experiencing disease progression or patients that died prior to experiencing cognitive failure will be considered as having had a competing event. Progressive disease frequently causes cognitive decline, and the goal of this study is to assess the impact of the radiation treatment itself on cognitive decline.
- 10.2 Definitions of secondary endpoints:
 - 10.2.1 Local control and distant control in the brain will be measured by contrast-enhanced brain MRI scan using Response Assessment in Neuro-Oncology (RANO)Criteria, as follows [50].
 - 10.2.1.1 Complete Response (CR): Requires all of the following 1) complete disappearance of all enhancing measurable and non-measurable disease sustained for a minimum of 4 weeks; 2) no new lesions; 3) stable or improving nonenhancing (T2/FLAIR) lesions; 4) patients must be off corticosteroids (or on physiologic replacement doses only); and 5) stable or improved clinically.
 - 10.2.1.2 Partial Response (PR): Requires all of the following: 1) ≥50% decrease compared with baseline in the sum of products of perpendicular diameters of all measurable enhancing lesions sustained for at least 4 weeks; 2) no progression of non-measurable disease; 3) no new lesions; 4) stable or improved non-enhancing (T2/FLAIR) lesions on the same

or lower dose of corticosteroids compared with the baseline scan; 5) stable or improved clinically.

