 - 10.3.2 Inflammatory Markers: Serum specimens collected within the first five fractions of treatment and at each follow-up visit will be analyzed using commercially-available ELISAs from R&D Systems, Inc. for the following inflammatory biomarkers: interleukin 1 (IL-1), interleukin 6 (IL-6), and tumor necrosis factor alpha (TNFα). These markers will be assayed in the laboratory of the Study Chair.
 - 10.3.3 Hormone and Growth Factors: Serum specimens collected within the first five fractions of treatment and at each follow-up visit will be analyzed using commercially available Enzyme Linked Immunosorbant Assays (ELISAs) for the following hormone and growth factors: glucocorticoids (e.g., cortisol), gonadal steroids (e.g.,

estradiol, testosterone, progesterone), growth hormone, human chorionic gonadotropin (hCG), insulin-like growth factor-1 (IGF-1), and neuronal growth factor (NGF). These assays will be performed in the laboratory of the Study Chair.

- 10.3.4 A portion of the serum and DNA will initially be analyzed as described above. According to patient consent information, the remaining body fluid biospecimens will be stored as de-identified frozen specimens in locked storage at -70°C in the laboratory of the Study Chair. As new protocols are developed they will be presented for IRB review and approval.
- 10.3.5 Return of Genetic Testing Research Results: Because the results generated by the genetic testing included in this section are not currently anticipated to have clinical relevance to the patient or their family members, the genetic results will not be disclosed to the patients or their physicians. If at any time, genetic results are obtained that may have clinical relevance, IRB review and approval will be sought regarding the most appropriate manner of disclosure and whether or not validation in a Food and Drug Administration (FDA) Clinical Laboratory Improvement Amendments (CLIA)-certified setting will be required. Sharing of research data with individual patients should only occur when data have been validated by multiple studies and testing has been done in CLIA-approved laboratories.

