- 12.3 Primary Analysis: The analysis will be performed on the intention-to-treat principle. Considering those patients who are not evaluable as treatment failures. We will use the methods of Gooley et al. [52]to estimate the cumulative incidence of cognitive failure in each treatment arm, considering progressive disease and death before cognitive failure as competing events. We will estimate the cumulative incidence of cognitive failure at 4 months with 95% confidence intervals. We will use the methods of Fine and Gray [53]to test for a difference between treatment arms with respect to the cumulative incidence of cognitive failure, considering progressive disease and death before and death before and death before cognitive failure as competing events. We will use the methods of Fine and Gray [53]to test for a difference between treatment arms with respect to the cumulative incidence of cognitive failure, considering progressive disease and death before cognitive failure as competing events. Our model will include treatment arm and the stratification factors used at randomization.
- 12.4 Secondary Analysis:

We will repeat the primary analysis on only those patients considered evaluable. All the secondary analyses described below will be performed using all patients as well as using only evaluable patients. We will estimate the cumulative incidence of local failure using the methods of Gooley et al. considering death as a competing event. We will model the time to local failure using the methods of Fine and Gray to test for differences between treatment arms, considering death as a competing event. Our model will include treatment arm and the stratification factors used at randomization, as well as selected dosimetric parameters. We will similarly analyze time to distant failure.

We will use the product limit estimator of Kaplan and Meier [54] to estimate overall survival stratified by treatment arm. We will also use Cox proportional hazards regression [55] to model overall survival as a function of treatment arm and the stratification factors used at randomization.

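### The biomarker model for neurocognitive decline ignores event time and competing events, so marker associations can be biased in either direction and power is lost over long follow-up

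*Combined protocol and SAP*

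**What the plan says.** Section 12.4 of the combined protocol and SAP covers ApoE genotype, the inflammatory markers and the hormones and growth factors in one sentence: "We will use logistic regression methods to model the logit of the probability of neurocognitive decline" as a function of those markers. For this model it does not define decline, name a time point, require a length of follow-up or say what happens to a patient who progresses or dies first.

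Other sections bear on the question:

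- Objective 3.3.2 asks whether the inflammatory markers "may prove to be predictors of radiation induced neurocognitive decline". Objectives 3.3.1 and 3.3.3 ask the same of ApoE and the hormones.
- Section 10.1.1 defines cognitive failure by the reliable change index (RCI) and states: "Patients experiencing disease progression or patients that died prior to experiencing cognitive failure will be considered as having had a competing event". It gives the reason: "Progressive disease frequently causes cognitive decline".
- Section 12.3 analyses the primary endpoint on the intention-to-treat principle: "Considering those patients who are not evaluable as treatment failures".
- Section 12.4 adds: "All the secondary analyses described below will be performed using all patients as well as using only evaluable patients". Under section 12.2 an evaluable patient has received the assigned treatment and "completed baseline and at least one follow-up neurocognitive testing".
- Section 9.2 continues cognitive testing to two years and states no stop at progression.
- Section 10.3.2 on the inflammatory markers reads: "Serum specimens collected within the first five fractions of treatment and at each follow-up visit will be analyzed". The model does not say which draw is used.

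**The concern.** The primary endpoint is built to separate the effect of radiation from that of progression, and the correlative objectives ask about the same radiation effect. The biomarker model uses neither the time of decline nor the order of decline and progression.

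Two problems follow:

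- **Bias.** A patient who progresses early has less time in which to decline from treatment. If a marker is related to progression, the yes/no outcome differs by marker level even when the marker has no effect on cognition. The sign depends on a coding choice that the plan leaves open and that could be made after the data are seen.
- **Power.** Over long follow-up most patients have had one event or the other, and much of the information lies in when decline occurred. A yes/no outcome discards it. This affects every marker, including those unrelated to progression.

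**Working it through.** **Inputs from the documents (section 12.2).** Cognitive failure at 4 months is 45% with IMRT and 30% with IMPT, times are exponential, and there are 60 evaluable patients.

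- Hazards: −ln(0.55)/4 = 0.1495 and −ln(0.70)/4 = 0.0892 per month.
- Medians: ln 2/0.1495 = 4.64 and ln 2/0.0892 = 7.77 months. The plan's 4.6 and 7.8 reproduce.
- Mean decline hazard: λ = (0.1495 + 0.0892)/2 = 0.1193 per month.

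The plan states no figure for the biomarker analysis. Its 43 events belong to the primary endpoint.

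**Assumptions (not in the documents).** The median time to progression or death is 10 months, so μ = ln 2/10 = 0.0693 per month. The marker is standard normal, tests are two-sided at 5%, and event times are known exactly.

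**Step 1: who is in the no-decline group.** At an average marker value the decline probability is F(t) = λ/(λ+μ) × (1 − e^−(λ+μ)t), with λ+μ = 0.1886 and λ/(λ+μ) = 0.6325. For 60 patients:

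| Month | Event-free share | Declined first | Progressed or died first | Neither |
|---|---|---|---|---|
| 4 | 0.470 | 20.1 | 11.7 | 28.2 |
| 12 | 0.104 | 34.0 | 19.8 | 6.2 |
| 24 | 0.011 | 37.5 | 21.8 | 0.6 |

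By 24 months almost everyone without a recorded decline is a competing event, so their coding decides the result.

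**Step 2: a marker with no cognitive effect and a progression hazard ratio of 2.0 per SD (simulated odds ratios).**

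| Coding of competing events | 4 months | 12 months | 24 months |
|---|---|---|---|
| Non-decline | 0.87 | 0.64 | about 0.5 |
| Excluded | 1.15 | 1.39 | 1.7 |
| Failure | 1.51 | 1.80 | 2.1 |

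With non-decline coding the marker is significant in about 7%, 34% and 62% of trials at the three horizons. At 24 months the cause-specific Cox hazard ratio is near 1.0, with about 5% rejection. The 24-month figures for the other two codings are imprecise: in about half of trials (0.989^60 = 0.52) nobody is left event-free and the model cannot be fitted.

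**Step 3: closed-form check with a binary marker.** Take a 9-month median in marker-negative patients (μ = 0.0770), and let the marker double the progression hazard only.

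- F(24), negative: 0.1193/0.1963 × (1 − e^−4.71) = 0.602.
- F(24), positive: 0.1193/0.2733 × (1 − e^−6.56) = 0.436.
- Odds ratio, non-decline coding: (0.436/0.564)/(0.602/0.398) = 0.51. At 4 months the same steps give 0.290 against 0.331, an odds ratio of 0.83.
- Excluding these patients gives 1.19 at 4 months. Coding them as failures gives 1.66.
- Cause-specific Cox gives about 1.01 at 4, 12 and 24 months. Fine-Gray gives 0.87, 0.72 and 0.67.

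Over medians of 6 to 12 months and progression hazard ratios of 1.5 to 3, non-decline coding gives 0.62 to 0.93 at 4 months and 0.34 to 0.68 at 24 months. At 4 months, exclusion gives 1.07 to 1.76 and failure coding 1.24 to 3.50.

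**Step 4: power for a true cognitive hazard ratio of 1.5 per SD with no progression effect (10-month median, non-decline coding).**

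| Month | Logistic | Cause-specific Cox |
|---|---|---|
| 4 | 37% | 41% |
| 12 | 39% | 58% |
| 24 | 32% | 64% |

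**The case against.** The strongest reply is that the plan does not commit the error. A reader might infer that early progressors and deaths are counted as non-decliners, so that markers of aggressive tumour would look neuroprotective. The documents do not support that. No coding is stated, and other text points elsewhere: the primary analysis counts non-evaluable patients as failures, the evaluable set drops patients with no follow-up test, and testing may continue after progression. Two of the three codings make the same marker look harmful. Only inflammation is linked to the tumour, through mass effect (section 5.2.2) and only as a possibility. Nothing in the documents says that ApoE or any hormone speeds progression. All of this stands, and it is why the point claims no direction.

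The horizon matters too. The only landmark the plan names for cognitive failure is 4 months, where bias under non-decline coding and the loss of power are both small. That also stands, but the model is not tied to 4 months and testing runs to two years, so the larger figures are not excluded.

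A logistic model at a fixed, defined horizon is a legitimate prediction analysis, and these are correlative objectives. Both are true, but this model has no fixed horizon, and the objectives name decline caused by radiation.

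A reader might also infer an overfitted model with about 13 marker terms. The plan does not say that they enter together.

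**Conclusion.** The point holds as one about method. An untimed yes/no model does not fit an objective about radiation-induced decline when the protocol treats progression and death as competing events. For a marker linked to progression, the association can be spurious in either direction. For any marker with a true effect, discarding event times halves power at 24 months (64% to 32%) and costs only about 4 percentage points at 4 months.

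These sizes rest on the assumed competing median, marker effects and exact event times. Two-monthly visits would blur the timing and probably narrow the Cox advantage. The simulation also makes decline and progression independent given the marker. If they share an unmeasured cause, a cause-specific hazard ratio need not be exactly 1 for a null marker.

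The primary conclusion is unaffected. This is a cheap improvement to a correlative analysis.

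**What to change.** Replace the logistic model in section 12.4 with a cause-specific Cox model:

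- **Outcome:** time to cognitive failure by the RCI rule of section 10.1.1, censored at progression or death.
- **Covariates:** the first-draw marker value, one marker at a time, adjusted for arm and the stratification factors.
- **Missing data:** a stated rule for patients with missing tests, in both the all-patient and the evaluable set.
- **Presentation:** cumulative incidence of cognitive failure by marker level alongside the hazard ratio.

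Do not simply reuse the Fine-Gray model of the primary analysis. A subdistribution hazard ratio moves with the marker's effect on progression, so the pattern stays. Analyses of follow-up draws as time-varying covariates are optional.

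The cost is SAP wording, since the data are already collected. The downside is that the result is a hazard ratio rather than a probability of decline, which the cumulative incidence curves partly make good.
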